4.0 Study Objectives, Design and Procedures

4.1 Objectives

The primary objective of this study is to examine the effect of LCIG relative to that of optimized medical treatment (OMT) on non-motor symptoms associated with advanced Parkinson's disease (PD) as assessed by the Non-Motor Symptoms Scale (NMSS) Total Score and the Modified Parkinson's Disease Sleep Scale (PDSS-2) Total Score.

4.2 Design Diagram

This is a Phase 3b, open-label, randomized multicenter 26-week study comparing LCIG to OMT for the treatment of non-motor symptoms in subjects with advanced Parkinson's disease.

The study will consist of three sequential parts:

Part 1: Screening period. The screening period will consist of three visits, Visit 1 (V1), Visit 2 ([V2] [optional]) and the Randomization Visit (V3) in which the subject will be assessed to determine eligibility. The duration of the Screening Period can be between 30 – 67 days to accommodate the required procedures, training and collection of diaries, and to allow for stabilization of anti-PD medications and medications to treat NMS. All anti-PD medications and medications to treat NMS are required to be stable for a minimum of 30 days prior to randomization.

Part 2: Treatment period. Those subjects randomized to OMT at the end of V3 will remain on their current optimized regimen. The day after randomization will be considered Day 1 of their treatment period and subjects will have study visits at the end of Weeks 2, 6, 12, and 26. All subjects randomized to the LCIG group should have all anti-PD medications, with the exception of levodopa formulations, tapered off within 14 days after randomization. Optional nasojujunal and/or percutaneous endoscopic gastrostomy with a jejunal tube (PEG-J) placement will then be placed. After that, the subject may begin initiation and titration of LCIG infusion to be adjusted to obtain the optimal clinical response in 14 days. The day of initial NJ or PEG-J placement will be considered Day 1 for subjects in the LCIG group. Study visits happen at the end of Weeks 2, 6, 12, and 26.

Part 3: Extension Period. Subjects in the United States or South Korea from both treatment arms who complete the 26 week study may continue into the Extension Period of the study. South Korea subjects in the LCIG arm will have study drug dispensation every 4 weeks and will have study visits every 6 months. South Korea subjects from the OMT arm will undergo the NJ (optional) and PEG-J procedures, titration, plus have visits at 2 weeks, 6 weeks, 3 months and 6 months post NJ or PEG-J. Subjects will then continue to receive study drug every 4 weeks and will have study visits every 6 months until Duodopa is commercially available.

United States subjects in LCIG arm will continue to have study drug dispensation every 4 weeks and will have study visits at 3 and 6 months, or the day prior to transition to commercial if that happens before the scheduled study visits. United States subjects from the OMT arm will undergo the NJ (optional) and PEG-J procedures, titration, plus have visits at 2 weeks, 6 weeks, 3 months and 6 months post NJ or PEG-J, or the day prior to transition to commercial if that happens before the scheduled study visits. Subjects will receive study drug every 4 weeks. The Extension Period will last for a maximum of 6 months to allow for continuity of care while the transition to commercially available drug occurs.

Part 4: Follow-up period. For subjects who elect to discontinue LCIG treatment at any time during the study, the PEG-J tube will be removed following the End of Study activities. A follow-up clinic visit will occur approximately 1 week later. For study subjects who complete participation in the study and will continue to receive LCIG, subjects will return every 6 weeks to return used LCIG cassettes and be dispensed cassettes. Additional visits every 12 weeks from Week 26 will be scheduled to monitor subject safety and allow for drug resupply until the subject transfers to commercial LCIG.

Figure 1. Study Design Schematic (All Countries Except for United States and South Korea)

[figure not shown]
[figure not shown]
[figure not shown]

Figure 2. Study Design Schematic (United States)

Extension Period:

OMT Subjects

LCIG Subjects

[figure not shown]
[figure not shown]
[figure not shown]

Figure 3. Study Design Schematic (South Korea)

[figure not shown]

Extension Period:

OMT Subjects

LCIG Subjects

4.3 Sample Size

Approximately 88 subjects will be enrolled into the study and randomized in a 1:1 ratio to either optimized medical treatment or LCIG. There are no data on NMSS or PDSS-2 available from randomized trials comparing LCIG and OMT. Interim data from ongoing Phase 3b Study M12-920 showed that the improvement in NMSS total score from baseline to Week 12 is 24.8 in the LCIG group with standard deviation of 24. Results from Zibetti et al (2013) showed that the improvement in PDSS 2 total score after an average of 3.5 months of LCIG treatment was 13.1. The standard deviation was not provided and is estimated to be 12.2 assuming the correlation between baseline and follow-up visits is 0.5.

The significance level for this study is 0.05. For sample size determination, it is assumed that the improvement in the OMT group is 33% of the LCIG group, i.e., the improvement is 8.2 on NMSS total score and 4.3 on PDSS-2 total score, and that the correlation between these 2 measures is 0.5. Simulation showed that a study with 37 subjects per

group will have 90% power to declare statistical significance on at least one of these 2 alternative primary endpoints after multiplicity adjustment using Hochberg procedure. It is further assumed that 10% of randomized subjects in either treatment group will not provide post-randomization efficacy assessment. Additional simulations showed that 44 subjects per group will provide 90% power in the sensitivity analysis using baseline observation carried forward for subjects without post-randomization assessment. Therefore the total planned enrollment is decided to be 88 subjects.

4.4 Interim Analysis

After all randomized subjects have completed the 26-week Treatment Period, or have discontinued during the Treatment Period and those randomized to LCIG have completed Follow-up Period, the primary objective of the study will have been fulfilled. A database lock will occur. Primary analyses of efficacy and safety data comparing LCIG and OMT arms will be conducted at that time.

4.5 Efficacy and Health-Related Outcome Measures

4.5.1 Non-Motor Symptoms

The burden of non-motor symptoms of Parkinson's disease will be evaluated using the Non-Motor Symptom Scale (NMSS) and Modified Parkinson's Disease Sleep Scale (PDSS-2).

4.5.2 Motor Symptoms

Motor symptoms will be assessed by Unified Parkinson's Disease Rating Scale (UPDRS) Parts III and IV.

4.5.3 Health-Related Outcomes

Health-related outcomes will be assessed by the following measures.

- Parkinson's Disease Questionnaire-8 (PDQ-8)
- Clinical Global Impression – Change (CGI-C)

- Unified Parkinson's Disease Rating Scale (UPDRS Parts I and II)
- Patient Global Impression of Change (PGIC)
- Parkinson Anxiety Scale (PAS)
- Geriatric Depression Scale (GDS-15)
- King's PD Pain Scale

A description of each measure is included in Protocol Section 5.3.1.1 Study Procedures. Each measure will be assessed at the times indicated in the relevant study activities flow chart ([Appendix A](#)).

4.6 Safety Measures

Safety and tolerability over the course of the study will be assessed by the following measures.

- Adverse event monitoring
- Neurological exams
- Clinical laboratory evaluations (including special labs to detect vitamin deficiencies)
- Electrocardiogram
- Vital signs and weight
- Columbia Suicide Severity Rating Scale (C-SSRS)
- Minnesota Impulsive Disorders Interview (MIDI)
- Sleep Attacks Questionnaire (SAQ)

A description of each measure is included in Protocol Section 5.3.1.1 Study Procedures. Each measure will be assessed at the times indicated in the study activities flow chart ([Appendix A](#)).

5.0 Analysis Populations

Analyses will be performed utilizing the following datasets.

Intent-to-Treat Dataset

The intent-to-treat dataset will include all subjects who are randomized to the optimized medical treatment, and all subjects who are randomized to LCIG and received at least one dose of study drug. The intent-to-treat dataset will be used to summarize efficacy and health outcome measures.

Safety Dataset

The safety dataset will include all subjects who are randomized to the optimized medical treatment, and all subjects who are randomized to LCIG and have study device (NJ and/or PEG-J) placement. The safety dataset will be used to summarize safety data during the OMT and LCIG treatment period.

All Randomized Dataset

The all randomized dataset will include all subjects who are randomized to the optimized medical treatment, and all subjects who are randomized to LCIG treatment. The all randomized dataset will be used to perform sensitivity analysis.

6.0 Analysis Conventions

6.1 Statistical Significance

This is a randomized open-label study. Unless otherwise specified, statistical tests will be two-sided and the null hypothesis will be rejected at the significance level of $\alpha = 0.050$. *P* values will be rounded to three decimal points before assessing statistical significance. Adjustments for multiple comparisons for the two primary endpoints will be made using the Hochberg procedure. If the primary endpoints are statistically significant, a Hochberg procedure will be used to test the 3 key secondary efficacy variables.

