8.1.3 Efficacy Analysis

All efficacy analyses will be performed on the ITT dataset unless otherwise specified. Comparisons between OMT and LCIG groups will be performed with two-sided tests at the significance level of 0.050.

Unless otherwise specified, the "baseline" for efficacy variables is defined as the last assessment taken on or before the day of randomization, and the "final observation" refers to the last non-missing observation in the Treatment Period (including evaluations conducted within 2 days after the last dose of study drug for subjects randomized to LCIG).

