9.0 Efficacy and Health Outcome Analysis

9.1 General Considerations

This is a randomized open-label study. Unless otherwise specified, statistical tests will be two-sided and the null hypothesis will be rejected at the significance level of $\alpha = 0.050$. *P* values will be rounded to 3 decimal places before assessing statistical significance. Unless noted otherwise, all analyses will be performed with the Intent-to-Treat Dataset. Missing data will not be imputed unless otherwise specified.

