The primary efficacy variables will be the change from baseline to Week 26 in the NMSS and PDSS-2 total scores. They will each be estimated using PROC MIXED and a mixed-effect repeated measures model (MMRM) for the change from baseline to each scheduled visit. The model will include the fixed effects of treatment, country and visit, with baseline score as a covariate, and the baseline score-by-visit interaction. The unstructured covariance structure will be used to estimate the within subject variance-covariance structure and Satterthwaite's approximation will be used to estimate the denominator degrees of freedom. If the model fails to converge, the first order autoregressive (AR[1]) covariance structure will be substituted. If the model still fails to converge, the compound symmetry (CS) covariance structure will be substituted. Type III sum-of-squares and least-square (LS) means will be used for statistical evaluations. The LS mean and 95% confidence interval obtained from the model will be presented. The primary comparison will be the contrast between LCIG and optimized medical treatment at the Week 26 Visit. The primary null and alternative hypotheses may be expressed as:

$$H_0: \mu_{\text{LCIG}} = \mu_{\text{OMT}}$$

$$H_A: \mu_{\text{LCIG}} \neq \mu_{\text{OMT}}$$

Where μ_{LCIG} is the mean change from baseline to Week 26 for LCIG group in the NMSS (or PDSS-2) total score and μ_{OMT} is the mean change from baseline to Week 26 for OMT group in the NMSS (or PDSS-2) total score. The statistical tests at other visits will be considered secondary.

The change in the NMSS (or PDSS-2) total score to each planned visit and to the final visit will also be summarized by the following descriptive statistics: number of non-

missing observations, mean baseline score and standard deviation, mean visit score and standard deviation, median visit score and range, mean change from baseline and its standard deviation and standard error, median change from baseline and range. The hypothesis of change from baseline will be evaluated at each visit with a one-sample t-test.

The two-sided P values obtained from the MMRM model for NMSS total score change from baseline to Week 26 and PDSS-2 total score change from baseline to Week 26 will be adjusted for multiplicity using the Hochberg procedure. This method controls the family-wise error rate (FWER) at a pre-specified significance level ($\alpha = 0.05$). Specifically, the following steps will be followed:

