- If the larger of the 2 P values is ≤ 0.05 (i.e., both P values are ≤ 0.05), both primary endpoints are considered statistically significant.
- If the larger of the 2 P value is > 0.05 , then compare the smaller P value with 0.025. The second primary endpoint is statistically significant if the P value is ≤ 0.025 ; otherwise, neither primary endpoint is considered statistically significant.

The mean NMSS and PDSS-2 total scores at baseline, Week 6, Week 12 and Week 26 and the mean changes in NMSS and PDSS-2 total scores from baseline to Week 6, Week 12 and Week 26 will be summarized by domain. Each mean domain score as well as the percentage it represents of the NMSS and PDSS-2 total score will be presented.

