9.3 Additional Efficacy Analyses

Secondary Analysis of the Primary Efficacy Variables

Analysis of covariance (ANCOVA) analyses will be carried out on change from baseline to final NMSS total score and change from baseline to final PDSS-2 total score. The ANCOVA model will contain treatment and country as the main effects and baseline score as the covariate. Sensitivity analyses will be carried out on the above variables with the same ANCOVA model using all randomized subjects. In this analysis, Baseline

Observation Carried Forward (BLOCF) will be applied to subjects who do not have post-randomization assessment of NMSS or PDSS-2.

Analysis of Secondary Efficacy Variables

The MMRM model, and the descriptive statistic summary described for the NMSS and PDSS-2 total score will also be used to evaluate the change from baseline in each of the following efficacy endpoints:

- UPDRS Part II score
- Parkinson's Disease Questionnaire-8 (PDQ-8) summary index
- NMSS domain scores
- PDSS-2 domain scores
- UPDRS total score, Part I score, Part III score, Part IV score
- Parkinson Anxiety Scale (PAS) total and subscale scores
- Geriatric Depression Scale (GDS-15)
- King's PD Pain Scale total and domain scores

For CGI-C and PGIC, an analysis of variance (ANOVA) model containing treatment and country as the main effects will be carried out.

UPDRS Part II score, CGI-C score and PDQ-8 summary index are key secondary endpoints. If both primary efficacy variables are statistically significant after adjusting for multiplicity, the Stepwise Gatekeeping Procedure will be utilized and the 3 key secondary endpoints will be tested using the Hochberg procedure with significance level of 0.05. Specifically, the following steps will be followed:

- If the largest of the 3 P values is ≤ 0.05 (i.e., all 3 P values are ≤ 0.05), all 3 key secondary endpoints are considered statistically significant.
- If the largest of the 3 P value is > 0.05 , then compare the middle P value with 0.025. The second and third key secondary endpoints are both statistically significant if the middle P value is ≤ 0.025 .

- If the largest of the 3 P value is > 0.05 and the middle P value is > 0.025 , then compare the smallest P value with 0.0167. If the smallest P value is ≤ 0.0167 , then the third key secondary endpoint is statistically significant. Otherwise, none of the 3 key secondary endpoints can be considered statistically significant.

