12.0 Summary of Changes

This SAP contains no change in analysis from the latest version of the protocol (Protocol Amendment 4).

The changes in this SAP from SAP V1.0 is: Per protocol amendments, subjects from South Korean/United States who complete the 26-week clinical study will have the option to enter an extension of the study. This SAP added the description for Extension Period analyses.

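### P values are rounded to three decimals before the Hochberg comparison, so the primary cutoffs become P < 0.0505 and P < 0.0255 and the claimed error control at 0.05 is not strictly met (excess at most about 0.001)

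*SAP*

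**What the plan says.** - **Rounding rule.** SAP 6.1 sets two-sided tests at 0.050, then says that P "values will be rounded to three decimal points before assessing statistical significance", directly before it names Hochberg for the two primary endpoints. SAP 9.1, which governs all efficacy analyses, repeats that P "values will be rounded to 3 decimal places before assessing statistical significance".
- **Primary decision rule.** SAP 9.2 and 9.5 declare both primaries significant if the larger P is at most 0.05. Otherwise the instruction is: "then compare the smaller P value with 0.025". Of the procedure, SAP 9.2 says: "This method controls the family-wise error rate (FWER) at a pre-specified significance level", given as 0.05.
- **Key secondaries.** If both primaries are significant, three key secondaries are tested by Hochberg at 0.05, 0.025 and, at the last step, "then compare the smallest P value with 0.0167" (SAP 9.3, repeated in 9.5).
- **Protocol.** Section 8.1.3 specifies "two-sided tests at the significance level of 0.050", and 8.1.3.1 gives the same two primary cutoffs. The protocol text provided has no rounding rule. SAP 12.0 states: "This SAP contains no change in analysis from the latest version of the protocol".

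**The concern.** As worded, rounding is part of the decision and not a display convention. Because the cutoffs are inclusive, rounding to the nearest 0.001 moves each primary cutoff up by half a unit in the third decimal. The SAP's claim of error control is made for the cutoffs as printed, not for the looser ones.

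Rounding turns a failed trial into a success in two situations:

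- the larger P lies between 0.05 and 0.0505 and the smaller is above 0.025;
- the smaller P lies between 0.025 and 0.0255 and the larger is above 0.05.

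It also opens the gate to the key secondaries whenever the larger P lies between 0.05 and 0.0505. In each case the reported conclusion would depend on the rounding sentence and would be hard to defend against the stated alpha.

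**Working it through.** **Inputs (SAP 4.3, 6.1, 9.2).** Alpha 0.05 two-sided; cutoffs c1 = 0.05 (larger P) and c2 = 0.025 (smaller P); improvement on LCIG 24.8 (NMSS) and 13.1 (PDSS-2), on OMT 8.2 and 4.3; SD 24 and 12.2; correlation 0.5; 37 or 44 per arm.

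**Effective cutoffs.** P = 0.0504999 rounds to 0.050 and passes; 0.0505001 rounds to 0.051 and fails. P = 0.0254999 rounds to 0.025 and passes; 0.0255001 rounds to 0.026 and fails. So c1 becomes 0.0505 and c2 becomes 0.0255.

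**The plan's own figure.** With both nulls true,

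FWER = P(smaller P < c2) + P(both P in [c2, c1)).

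For independent endpoints this is 1 − (1 − c2)² + (c1 − c2)².

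- As printed: 1 − 0.975² + 0.025² = 0.0500, which reproduces the stated 0.05.
- As rounded: 1 − 0.9745² + 0.025² = 0.050975.

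The excess is 0.000975.

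**Correlated endpoints, both nulls true** (bivariate normal rectangle probabilities):

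| Correlation | Unrounded | Rounded |
|---|---|---|
| 0 | 0.0500 | 0.0510 |
| 0.3 | 0.0493 | 0.0503 |
| 0.35 | 0.0491 | 0.0500 |
| 0.4 | 0.0488 | 0.0497 |
| 0.5 | 0.0480 | 0.0489 |
| 0.7 | 0.0456 | 0.0464 |

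The rounded rate exceeds 0.05 only when the correlation is below about 0.354.

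**One null true, correlation 0.5.** This is the false-claim rate on the null endpoint, by the noncentrality of the other endpoint:

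| Noncentrality | Unrounded | Rounded |
|---|---|---|
| 3 | 0.0436 | 0.0442 |
| 4 | 0.0484 | 0.0490 |
| 6 | 0.0500 | 0.0505 |

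Noncentrality 3 is about the planned effect at 37 per arm: (24.8 − 8.2)/(24·√(2/37)) = 2.97 for NMSS and (13.1 − 4.3)/(12.2·√(2/37)) = 3.10 for PDSS-2.

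**Power.** Simulation with two-sample t tests gives 90.6% on at least one primary at 37 per arm, in line with the stated 90%. The effect of rounding under the planning assumptions (normal approximation, complete data) is:

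| Per arm | Success, unrounded / rounded | Both significant, unrounded / rounded |
|---|---|---|
| 37 | 0.9132 / 0.9144 | 0.7705 / 0.7719 |
| 44 | 0.9524 / 0.9532 | 0.8500 / 0.8510 |

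Rounding therefore changes the trial verdict with probability about 0.12 percentage points at 37 per arm and 0.07 at 44 (differences taken before rounding to four places). It opens the secondary gate with probability about 0.14 and 0.11 points.

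**Key secondaries.** At the third step a three-decimal P meets a four-decimal cutoff. A P between 0.0165 and 0.0167 rounds to 0.017 and fails 0.0167, so this step is slightly too strict. With all three nulls true, rounding lowers the error rate: 0.0493 to 0.0488 by simulation for independent endpoints, and 0.0454 to 0.0450 at an assumed correlation of 0.5. This does not hold in general, because the first two steps are loosened. If one secondary is certain to be rejected, the other two face the same 0.05 and 0.025 rule as the primaries, and the independent-endpoint result above applies (0.0500 to 0.0510).

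**The case against.** The best defence is that this does not matter in practice. At the planning correlation the rounded error rate is 0.0489 with both nulls true, and 0.0442 with one null true and the other endpoint near its planned effect. Low correlation is also unlikely, since NMSS has a sleep/fatigue domain, PDSS-2 measures sleep, and the same blinded central raters administer both. The primary P values rest on Satterthwaite's approximation, so 0.0500 against 0.0505 is finer than the method's accuracy. The rule is prespecified and mechanical, and leaves the analyst no discretion. **All of this stands, and it is why the point is minor.** It does not make the claim of control true: SAP 9.2 attaches no condition on correlation, and prespecifying a looser cutoff makes it transparent without restoring the stated alpha.

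A second argument is that the step rules in SAP 9.2, 9.3 and 9.5 do not mention rounding, and the four-decimal 0.0167 suggests they were meant for P values as the model gives them. That may have been the intention. However, 6.1 and 9.1 are general rules with no exemption, so the literal reading is that they apply.

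Third, the SAP may elaborate where the protocol is silent, so the no-change statement in SAP 12.0 is not a plain contradiction. That is fair. The rounding sentence does alter which P values count as significant, but the concern does not depend on SAP 12.0.

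**Conclusion.** The concern holds and is minor. As written, the primary cutoffs are P < 0.0505 and P < 0.0255, and the family-wise error rate is not strictly held at 0.05. The largest excess is 0.000975, with both nulls true and independent endpoints; with one null true and the other endpoint overwhelmingly effective, it is 0.0005. Under the planning correlation and effects, the error rate stays below 0.05 even with rounding.

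These figures assume bivariate normal test statistics and P values that are accurate as computed. The mismatch at 0.0167 is a separate inconsistency; that step becomes stricter and does not inflate error.

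**What to change.** Replace the rounding sentences in SAP 6.1 and 9.1 with: *Significance is assessed on unrounded P values against 0.05, 0.025 and 0.05/3; P values are rounded to three decimals for display only.* In SAP 9.3 and 9.5, write the third key-secondary cutoff as 0.05/3.

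The cost is two sentences and one cutoff in two places, with no new analysis and about 0.1 percentage points of planned power. A primary P between 0.0500 and 0.0505, or between 0.0250 and 0.0255 at the second step, would no longer pass. A key-secondary P between about 0.0165 and 0.0167 at the third step would now pass. The maximum error rate for the two primaries returns to 0.0500 under the same bivariate normal assumption. The edit should be made before results are known, so that it cannot appear driven by the outcome.
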